7.5.2 Cutaneous safety

Analyses of the local tolerability on the face will be based on SAF population; and the analyses of the local tolerability on the trunk will be based on SAFT population.

Local tolerability variables (erythema, scaling, dryness, stinging/burning) will be summarized at Baseline, each post-baseline visit, "Worst" score, and "Final" score. "Worst" score is the highest severity score observed during post-baseline period for a subject. "Final" score is the last data observed during the post-baseline period for a subject. In addition, the number and percentage of subjects with a local tolerability score worsened from baseline will be summarized descriptively at each post-baseline visit, "Final" scores, and "Worst" score.

Additionally, subjects with a local tolerability score worse than the Baseline score will be summarized graphically at each post-Baseline visit including "Final" scores and "Worst" score.

Summary statistics by treating the severity scale as continuous outcome will also be presented.

Subgroup analyses by Age Group (<18 years, >=18 years), Race (white, non-white), Gender (female, male), Country (Europe, USA), and Skin Phototype (I-III, IV-VI) will be provided.

7.5.3 Adverse events

A treatment-emergent adverse event (TEAE) is defined as an adverse event that occurred on or after the first study drug application.

TEAEs will be tabulated in frequency tables by System Organ Class (SOC) and Preferred Term (PT) based on the MedDRA dictionary. In addition, incidence of TEAE by quarter will be summarized for “Baseline to < Month 3” (1 to 89 days), “Month 3 to <Month 6” (90 to 179 days), “Month 6 to < Month 9” (180 to 269 days), “Month 9 to 1 Year” (≥ 270 days). The AE incidence for each time period will be calculated by the number of subjects with AE onset dates within each period divided by the number of subjects at risk at the start of each period. Additional summary tables and listings will be provided for adverse events that are considered serious (SAEs), related to the study drug, severe, leading to discontinuation and of special interest. For a given TEAE, a subject will be counted once even if he or she has experienced multiple episodes for that particular TEAE.

The AEs of Special Interest for this protocol are pre-defined as follows:

- Out-of-range laboratory results that are identified as clinically significant and related to the study drug(s) are AESIs.
- Related cutaneous AEs which lead to permanent treatment discontinuation.
- Suspicion of allergic reaction suspected to be related to the study drug.

The following TEAE summaries will be provided:

- Summary of overall AE(s)
- Frequency and percentage of subjects with AE(s) by System Organ Class (SOC) and Preferred Term (PT)
- Frequency and percentage of subjects with serious AE(s) by System Organ Class (SOC) and Preferred Term (PT)
- Frequency and percentage of subjects with related AE(s) by System Organ Class (SOC) and Preferred Term (PT)
- Frequency and percentage of subjects with related AE(s) by Preferred Term (PT)
- Frequency and percentage of subjects with AE(s) leading to discontinuation by System Organ Class (SOC) and Preferred Term (PT)
- Frequency and percentage of subjects with severe AE(s) by System Organ Class (SOC) and Preferred Term (PT)
- Frequency and percentage of subjects with AE(s) of special interest by System Organ Class (SOC) and Preferred Term (PT)

Summaries of overall Adverse Events and summaries of Adverse Events by System Organ Class (SOC) and Preferred Term (PT) will be presented by Age Group (<18 years, ≥18 years), Race (white, non-white), Gender (female, male), Country (Europe, USA) and Skin Phototype (I-III, IV-VI).

Furthermore, the chronology of TEAE will be assessed with respect to AE onset and AE duration. Descriptive statistics (N, minimum, medians and maximum) will be presented by Preferred Term for the following:

- Duration from the first dose date to AE onset date,
- Duration of AE from AE start date to AE stop date.

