3.2 Safety assessment

A safety assessment will be conducted for all subjects at the Screening visit (from the Informed consent signature) and every subsequent visit. The safety parameters are the recording of adverse events, laboratory safety tests, physical examination, vital signs and local tolerability scores on the face and on the trunk (0 [none] to 3 [severe]) for erythema, scaling, dryness, and stinging/burning.

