3.2.2 Adverse events

Adverse events (AEs) are to be monitored throughout the course of the clinical trial. All AEs are to be reported on the Adverse Event Form of the eCRF with complete information as required, including onset/end dates of AEs, severity of AEs, relationship to the study drug, serious AEs and AEs of special interest.

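### The TEAE definition in SAP 7.5.3 rests on onset alone and has no clause for an event that starts before first application and worsens or becomes serious on treatment

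*SAP*

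**What the plan says.** - **Definition.** SAP 7.5.3: "A treatment-emergent adverse event (TEAE) is defined as an adverse event that occurred on or after the first study drug application". Nothing is said about an event that is already present and changes on treatment.
- **Start of collection.** SAP 3.2: "A safety assessment will be conducted for all subjects at the Screening visit (from the Informed consent signature) and every subsequent visit". AEs with onset before the first application can therefore be in the database.
- **AE fields.** SAP 3.2.2 asks for complete information, "including onset/end dates of AEs, severity of AEs, relationship to the study drug, serious AEs and AEs of special interest". It does not say whether a worsening updates the existing record or opens a new one.
- **Timing variable.** For incidence by quarter, SAP 7.5.3 says: "The AE incidence for each time period will be calculated by the number of subjects with AE onset dates within each period", with the first quarter starting at day 1. The chronology summary, also in 7.5.3, uses "Duration from the first dose date to AE onset date".
- **Scope of the tables.** The overall, serious, related, discontinuation, severe and AESI tables stand under the line "The following TEAE summaries will be provided". An earlier sentence in the same section is worded differently: "Additional summary tables and listings will be provided for adverse events that are considered serious (SAEs), related to the study drug, severe, leading". That sentence goes on to name discontinuation events and AESIs. The table titles in Section 9 also refer to adverse events, not to TEAEs.

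**The concern.** The primary objective is long-term safety and there is no comparator arm, so TEAE incidence is a main result of the study. An event that begins between consent and first application, and becomes severe or serious once the cream is in use, is one that a treatment-emergent table would ordinarily be expected to show. A rule based on onset alone leaves it out. Compared with a definition that includes worsening, this rule can only lower the counts.

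The SAP does treat change from baseline as a safety signal elsewhere. For local tolerability, "the number and percentage of subjects with a local tolerability score worsened from baseline will be summarized descriptively" (Section 7.5.2), and Section 7.5.4 plans laboratory shift tables. The AE definition has no counterpart. The gap is limited to AEs that start after consent, are still ongoing at first application and then change. It does not concern skin conditions already present before consent.

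**Working it through.** The plan gives no figure to reproduce. The check is a reading of the sections against each other, with one line of arithmetic for scale.

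**1. Is the rule really onset-based?** The word used in the definition could loosely cover a worsening. The analyses built on it do not allow that. Take an AE with onset before the first application that becomes severe on treatment. Its onset date is before day 1, so it falls in none of the four quarters. Its time from first dose to onset would be negative. Both analyses work only if a TEAE has its onset on or after first application.

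**2. Can such events exist?** Yes. Safety assessment runs from consent (3.2). Laboratory tests (3.2.3) and physical examinations (3.2.5) are done at Screening, and abnormal results are judged for clinical significance.

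**3. Which tables are affected?** If the TEAE heading in 7.5.3 governs, the event is missing from the overall table, the SOC/PT tables and the serious, related, discontinuation, severe and AESI tables. If the other 7.5.3 sentence and the Section 9 titles govern, the serious, related, severe, discontinuation and AESI tables would cover all AEs. They would then also count events that ended before any drug was applied, and might not agree with the TEAE totals. Section 9 gives the main SOC/PT table an adverse-event title too, although 7.5.3 makes it a TEAE table, so the titles look like shorthand. The text does not settle the matter.

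**4. Where does the event still appear?**
- Subject listings: Section 9 lists all eCRF data.
- Disposition: 7.1.1 takes the primary reason for discontinuation from the exit form with no TEAE filter, so a subject who stopped for an AE may be counted there.
- Tolerability: if the event shows as erythema, scaling, dryness or stinging/burning, 7.5.2 tabulates worsening from baseline whatever the AE onset date.

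**5. Scale.** Planned enrolment is 450 (Section 6). The documents give neither the share of subjects with an AE ongoing at first application (p) nor the share of those whose event worsens (w), so both are assumptions. Subjects affected = 450 × p × w.

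| p | w | Subjects | Share of 450 |
|---|---|---|---|
| 1% | 5% | 450 × 0.01 × 0.05 = 0.2 | 0.05% |
| 2% | 10% | 450 × 0.02 × 0.10 = 0.9 | 0.2% |
| 5% | 20% | 450 × 0.05 × 0.20 = 4.5 | 1.0% |

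The range is about 0.2 to 5 subjects. It counts all worsened events. The number in any single table, such as serious or AESI, would be a fraction of it.

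**The case against.** The strongest reply is that the outcome depends on an AE-recording convention that a SAP commonly leaves to the protocol. If sites enter an on-treatment worsening as a new AE with its own onset date, the definition already counts it and there is no undercount. This stands as a condition on the point. It does not remove the point: the SAP defines the TEAE flag, and a programmer working from 7.5.3 has no instruction for a worsened event kept under its old onset date.

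A second reply is that tolerability, laboratory shifts, disposition and listings already show worsening. This is right in part. The tolerability tables cover four signs only. They do not cover other skin events, allergic reactions, non-skin events or seriousness. Disposition gives the reason for stopping but not the event. Listings are not incidence.

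A reader might also infer that such an event disappears from every AE table, or that AESI counts are materially too low. The documents support neither. Table scope is worded inconsistently in 7.5.3 and Section 9, so total exclusion is not certain. All three AESI categories require a suspected or judged relation to study drug. An event that began before any exposure would ordinarily be judged related only through its worsening, so that route is narrow and its size is unknown.

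**Conclusion.** The point holds in limited form. As written, 7.5.3 classifies by onset and does not count as treatment-emergent an AE that starts between consent and first application and then increases in severity or becomes serious on treatment. Unless a worsening is recorded as a new AE, which this SAP does not state, the event is left out of the tables that 7.5.3 lists as TEAE summaries.

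The direction is certain (undercount only). The size is probably a few subjects at most, about 0.2 to 5 of 450, and rests wholly on assumed rates. The effect on overall TEAE incidence would be small, and no material effect on AESIs is shown. The change is worth making because safety is the primary objective and the correction is cheap. The unclear scope of the AE tables needs settling in any case.

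**What to change.** 1. In 7.5.3, define a TEAE as an AE with onset on or after the first application, or with onset before it that increases in severity or becomes serious on or after it. A change in judged relationship alone should not be a trigger, because it would make an event treatment-emergent with no change in its severity or seriousness.
2. For such events, use the date of worsening in the quarterly and chronology summaries where that date is recorded, and state what is done where it is not.
3. If the protocol or eCRF instructions already require a worsening to be entered as a new AE, say so in 7.5.3 and count the new record. Item 1 is then met without a new derivation.
4. Reconcile the TEAE heading in 7.5.3 with the earlier sentence on additional tables and with the Section 9 titles, so that each table and listing is marked as covering TEAEs or all AEs.

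The cost is a few sentences, one small change to the derivation and some retitled shells. TEAE rates may come out slightly higher.

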6 SAMPLE SIZE CONSIDERATION

Approximately 600 subjects will be screened to enroll 450 subjects worldwide, including the United States of America and Europe.

The exposure of subjects to CD5789 50 μ g/g cream follows internationally accepted guidelines for the assessment of clinical safety for products intended for chronic use. The International Conference on Harmonization E1a Guideline suggests that 300 subjects for six months or 100 subjects for one year should be evaluated for safety. This study was designed to ensure that at least 300 subjects will be exposed to CD5789 50 μ g/g cream for 6 months, and 100 subjects exposed for 1 year.

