7.4.6 Statistical and analytical issues

7.4.6.1 Handling of dropouts or missing data

In this study, summary statistics will be based on the observed data and no missing data imputation will be performed.

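### The quarterly adverse-event incidences in SAP section 7.5.3 cannot be compared with each other: exits within a period are ignored and the last period has no end

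*SAP*

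**What the plan says.** SAP section 7.5.3 defines a treatment-emergent event as "an adverse event that occurred on or after the first study drug application"; no end is given. It sets four periods: days 1 to 89, days 90 to 179, "180 to 269 days", and day 270 onwards. The last is labelled as running from month 9 to one year, but its day rule has no upper limit.

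Incidence in each period is "the number of subjects with AE onset dates within each period" "divided by the number of subjects at risk at the start of each period". The section does not say whether being at risk means in the study, on treatment or event-free. It counts a subject once for a given event, without saying whether that is once per period or once overall.

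Section 6 plans for 450 enrolled subjects and an exposure target of "at least 300 subjects will be exposed to CD5789 50 μ g/g cream for 6 months, and 100 subjects exposed for 1 year". No dropout rate is stated. Section 7 makes all analyses descriptive.

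**The concern.** Long-term safety is the primary objective (section 1.1.1), and this is the only AE incidence planned by time period. The four percentages will be read as a sequence, to see whether risk rises or falls over the year. That reading needs each figure to measure the same thing over the same length of time. Three features prevent it:

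- A subject who leaves one week into a quarter counts in the denominator as much as one who stays to its end. This lowers the figure in every period with exits, early or late.
- The last period is longer than the others and has no stated end. More days give more first onsets over the same denominator, which raises the figure.
- The event definition has no end. If being at risk means being on treatment, a subject who has stopped could still add an event to the numerator of a period whose denominator excludes that subject. This also raises the figure.

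A constant underlying rate could therefore show as a rise or a fall.

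**Working it through.** The SAP gives no AE rate or dropout rate, so it has no figure to reproduce. The check asks what the planned formula shows when the true rate is constant.

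**Period lengths, from section 7.5.3.** 89 − 1 + 1 = 89; 179 − 90 + 1 = 90; 269 − 180 + 1 = 90. If the last period is closed at day 365 (the Week 52 target day in section 7.9), 365 − 270 + 1 = 96.

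**Assumptions.** The AE hazard λ is constant, with a 90-day risk of 10%, so λ = −ln(0.90)/90 per day. Event-free subjects leave at a constant hazard μ, independent of AE risk. Four exit rates per 90 days are used:

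- 5% and 10% are plain assumptions.
- 18.4% is the rate that takes 450 to 300 in two equal quarters: 1 − √(300/450).
- 42.3% is the rate that takes 300 to 100 in two equal quarters: 1 − √(100/300).

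The last two treat the section 6 minimums as actual retention. They serve as a bound, not a forecast.

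**Formula.** Over L days the planned figure is expected to be λ/(λ+μ) × [1 − exp(−(λ+μ)L)]. The risk without exits is 1 − exp(−λL).

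Example with 10% exits and L = 90: λ = μ, so the figure is 0.5 × (1 − 0.90 × 0.90) = 9.50%, against a true 10%.

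| Exits per 90 days | Planned figure, 90 days | Against true 10% | Planned figure, 96 days | Against true 10% |
|---|---|---|---|---|
| 0% | 10.00% | 0 | 10.63% | +6.3% |
| 5% | 9.75% | −2.5% | 10.35% | +3.5% |
| 10% | 9.50% | −5.0% | 10.06% | +0.6% |
| 18.4% | 9.06% | −9.4% | 9.58% | −4.2% |
| 42.3% | 7.73% | −22.7% | 8.09% | −19.1% |

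The 90-day understatement hardly depends on the assumed AE risk. For 90-day risks from 5% to 30% it is 2.4–2.5%, 4.8–5.0%, 9.0–9.4% and 21.8–22.9% at the four non-zero exit rates.

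**Actuarial cross-check at the section 6 minimums.** 300 × √(1/3) = 173 subjects start the last quarter and 73 leave during it. Removing half the exits gives a denominator of about 136.6. 136.6/173.2 = 0.789, so the planned figure is about 21% too low, in line with the model.

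**Direction of the false trend.**

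- Equal exits of 5% in every quarter: 9.75% in a 90-day quarter, then 10.35% in the last. 10.35/9.75 = 1.06, a spurious rise of about 6%.
- Equal exits of 10%: 10.06/9.50 = 1.06, again a rise of about 6%.
- Retention at the section 6 minimums: about 9.06% in the first two quarters and 8.09% in the last. 8.09/9.06 = 0.89, a spurious fall of about 11%. (The first quarter is treated here as 90 days rather than 89.)

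For a 96-day last period, the two effects cancel against the true 90-day risk at about 11% exits per 90 days. If events were collected to day 395 (126 days, an assumption), the last figure would be 13.71% with no exits (+37%), and break-even would need about 39% exits.

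**Does person-time remove it?** Under the same model, expected first events per starting subject are λ/(λ+μ) × [1 − exp(−(λ+μ)L)], and expected person-time is [1 − exp(−(λ+μ)L)]/(λ+μ). Their ratio is λ, whatever μ or L.

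**The case against.** The strongest defence has four parts.

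- The plan already drops earlier leavers by starting each quarter afresh instead of dividing by the whole safety population, and it states the rule openly. This stands. Only exits within a quarter remain, and at 5–10% per quarter they are a small matter.
- Nothing inferential rests on the table. This also stands, and it limits the severity.
- The one-year label and the 52-week treatment period imply an end, and how long events are collected after treatment is commonly left to the protocol, which is not at hand. This stands in part. The SAP describes no long off-treatment follow-up, so the 126-day case is only illustrative. The label and the day rule still disagree within section 7.5.3.
- Attrition will be visible from treatment duration (section 7.5.1.2) and from the disposition table by study duration (section 9). That lets a reader see the problem but not correct it by period.

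Two stronger readings are tempting and not supported. A reader might infer that late risk is systematically understated, so that the table would show tolerability improving. The open end and any events counted after a subject leaves work the other way, and even exits of 5–10% give a rise. A marked fall appears when the section 6 figures are treated as an attrition curve, but those are minimum exposure targets. A reader might also infer that this table is the plan's only look at change over time. Section 7.5.3 also summarises time to onset by preferred term, and section 7.5.2 summarises local tolerability at each visit. Neither gives an exposure-adjusted AE rate.

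**Conclusion.** The point holds as a lack of comparability, not as a bias in a known direction. Ignoring exits lowers each period's figure by about 2.5–5% relative at an assumed 5–10% exits per quarter, and by about 9% to 23% only if retention fell to the section 6 minimums. The longer last period raises its figure by about 6% if it ends at day 365, and by more if events are collected for longer. The net trend can go either way.

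These sizes rest on a constant AE hazard, exits independent of AE risk, and exit rates that the SAP does not state. The severity is minor: the table is descriptive, but it bears on the primary objective and the remedy is cheap.

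**What to change.** In section 7.5.3, keep the crude percentage and make these changes:

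1. Add, for each period, subjects with a first event in that period per 100 subject-years. Person-time runs from the start of the period to the earliest of first onset in the period, end of exposure or follow-up, and end of the period. State which of exposure or follow-up applies; that also settles what being at risk means.
2. Count in the numerator only subjects who contribute person-time in that period, and say that a subject is counted once per period.
3. Give the last period an upper day that agrees with its one-year label.

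The cost is one extra column and slightly more programming. No new data are needed: AE onset dates are recorded (section 3.2.2), and application and visit dates already feed the duration variables (sections 7.5.1.1 and 7.5.1.2). The tentative table list in section 9 names no quarterly AE table, so it could be added in the same edit.

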2 STUDY DESIGN

This is a multi-center, open-label, non-comparative safety and efficacy study with 52 Weeks of treatment on the face and trunk for acne vulgaris.

Male and female subjects, 9 years of age or older, with an IGA of 3 and a minimum of 20 inflammatory lesions and 25 non-inflammatory lesions on the face, with a PGA of 3 and a minimum of 20 inflammatory lesions and 20 non-inflammatory lesions

on the trunk will be enrolled in the study (PGA and truncal lesions are optional inclusion criteria for children between 9-11 years old).

Approximately 450 subjects will be enrolled worldwide (Europe, USA). The total number of sites is expected to be approximately 30 to 40 with a minimal of 10 subjects per site.

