7 STATISTICAL METHODS AND DATA CONSIDERATIONS

For statistical analyses purpose, baseline is defined as the last measurement prior to the first application of the study drug.

No inferential statistical analysis is planned. Data to be collected will be summarized as observed.

For the summary statistics, the categorical variables will be summarized by frequency and percentage for each response category (N, %); and the continuous variables will be summarized using means, medians, minimum, maximum, and standard deviations.

All efficacy variables, DLQI/ C-DLQI, local tolerability, laboratory tests and vital signs will be summarized and analyzed by analysis visit. The methodology for defining analysis visit is provided in Section 7.9 “Analysis visit definition”.

SAS version 9.3 or above will be used for all statistical analyses.

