7.5.1.2 Treatment Duration

Treatment duration (day) is defined as “the date of the last application on face or the trunk, whichever is later, minus the date of the first application on face or the trunk, whichever is earlier, plus one”. If the date of the last application is not available, the date of the last visit will be used in calculation. If the date of the first application is not available, the date of the Baseline visit will be used in calculation.

Treatment duration will be summarized by descriptive statistics.

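### AE duration is defined only from start date to stop date, so AEs still ongoing leave the chronology summary by implication and its median is biased short for persistent AEs

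*SAP*

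**What the plan says.** The chronology part of SAP Section 7.5.3 describes TEAEs by time to onset and by duration. The output is fixed: "Descriptive statistics (N, minimum, medians and maximum) will be presented by Preferred Term for the following", and the duration item is "Duration of AE from AE start date to AE stop date". Section 9 lists a matching chronology table for the SAF population.

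The SAP does not mention AEs that have no stop date. Its general rule in Section 7 is "Data to be collected will be summarized as observed". Section 7.4.6.1 adds that "summary statistics will be based on the observed data and no missing data imputation will be performed"; that sentence sits under efficacy but is worded for the whole study.

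Section 3.2.2 has AEs recorded with complete information, "including onset/end dates of AEs, severity of AEs, relationship to the study drug". The dates needed for a better summary are therefore already collected.

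Elsewhere the SAP does say what to do when an end date is absent. For treatment duration, Section 7.5.1.2 states: "If the date of the last application is not available, the date of the last visit will be used in calculation". AE duration has no counterpart.

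**The concern.** Time to resolution is right-censored whenever an AE is still present at last contact. A start-to-stop definition with no rule for such AEs leaves them without a value. The loss is not random, because the longer an AE lasts, the more likely it is to outlive the subject's follow-up. What remains is a summary of AEs that resolved in time to be seen.

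The study's primary objective is safety over up to 52 weeks. A reader of the chronology table will take the median for a Preferred Term as how long that reaction lasts. For a persistent or late-onset reaction it would look shorter than it is, and nothing in Section 7.5.3 requires the table to show how many AEs were ongoing.

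**Working it through.** The SAP states no figure on this point, so there is none to reproduce. The check has two parts: the direction of the bias, and an illustration of its size.

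**Direction.** Let D be the AE's duration and C the follow-up remaining after onset, with D independent of C. The AE has a stop date only if D ≤ C. Given D = d, that probability is P(C ≥ d), which can only fall as d rises. Resolved AEs are therefore shifted towards short durations, and the bias cannot be upward.

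**Inputs.**
- From SAP Section 2, which describes an "open-label, non-comparative safety and efficacy study with 52 Weeks of treatment on the face and trunk": T = 52 × 7 = 364 days.
- Assumed: onset uniform over T, follow-up ending at T, no dropout, exponential durations with mean m = 60, 120 or 180 days.

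**Formulas.**
- Share ongoing = (m/T)(1 − e^(−T/m)).
- True median = m ln 2.
- Probability of being resolved with duration at most x: F(x) = 1 − m/T − e^(−x/m)[1 − (x + m)/T]. The displayed median solves F(x) = ½F(T).

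**Worked case, m = 60.**
- Share ongoing = (60/364)(1 − e^(−6.07)) = 0.1648 × 0.9977 = 0.164, so F(T) = 0.836 and half of it is 0.418.
- At x = 34.4: F = 1 − 0.1648 − 0.5637 × 0.7407 = 0.418, so 34.4 days is the displayed median.
- True median = 60 × 0.693 = 41.6 days.
- Shortfall = 1 − 34.4/41.6 = 17%.

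| Mean (days) | Ongoing | Displayed median | True median | Shortfall |
|---|---|---|---|---|
| 60 | 16% | 34 | 42 | 17% |
| 120 | 31% | 55 | 83 | 34% |
| 180 | 43% | 67 | 125 | 46% |

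**Sensitivity to the assumptions.**
- *Longer follow-up.* If AEs are followed for 90 further days, C is uniform from 90 to 454 days and the share ongoing is (m/T)(e^(−90/m) − e^(−454/m)). This gives 4%, 15% and 26%. The displayed medians become 39, 67 and 83 days, which are 5%, 20% and 33% short.
- *Short AEs.* With a true median of 14 days and uniform onset, about 6% are ongoing and the displayed median is 13.2 days, about 6% short.
- *Early onset* (exponential, mean 30 days, follow-up to day 365, simulation of 1,000,000 AEs per scenario). True medians of 7 to 30 days are essentially unchanged (29.7 to 30.0 for 30). A true 90 shows about 80, and a true 180 shows 116 to 127. The ranges cover exponential and lognormal durations (log SD 1).
- *Shape of the distribution.* With uniform onset and lognormal durations, a true 90 shows 63 and a true 180 shows 96; exponential durations give 58 and 77.

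**The case against.** Several points on the other side are sound.

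- **The exclusion is not written down.** A reader might infer that the SAP orders ongoing AEs to be dropped. It does not. The exclusion follows from a start-to-stop definition, the as-observed rule and silence on missing stop dates, and the explicit no-imputation sentence sits under efficacy. This limits how firmly the point can be put, but no other reading of the SAP supplies a duration for such an AE.
- **Follow-up rules may be in the protocol, which was not examined here.** If AEs are followed until they resolve, few will be ongoing and the bias shrinks, as the 90-day case shows. This stands, and it makes the size conditional.
- **Ongoing AEs remain visible elsewhere.** A reader might infer that persistent AEs vanish from the safety report. They do not. They count in every incidence table in Section 7.5.3 and appear in the AE listings in Section 9. For erythema, scaling, dryness and stinging/burning, Section 7.5.2 also reports the last observed score and its worsening from baseline. This stands and lowers the weight. It does not correct a median in the chronology table.
- **N is reported for both onset and duration.** The difference could reveal how many AEs lack a stop date. That works only if both rows count the same unit and the gap is not due to other missing dates, and Section 7.5.3 settles neither.
- **Kaplan-Meier has limits.** With about 450 subjects, many Preferred Terms will have few events and some medians will not be estimable. Repeat episodes within a subject are not independent. No method recovers a maximum longer than follow-up. All of this stands and shapes the fix.

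**Conclusion.** The point holds as a minor one. As written, the duration summary covers resolved AEs only, by implication, and its median is biased short. The bias is negligible for AEs that are short or followed to resolution, and can be substantial for AEs that persist or start late.

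The 17% to 46% range is an illustration. It rests on follow-up ending at week 52, uniform onset and mean durations of 60 to 180 days, none of which except the 52-week period comes from the SAP. It should not be read as the bias expected in this trial. Nor should the point be read as casting doubt on the primary safety results: duration is one descriptive line in a single-arm study with no inferential analysis, and AE incidence is unaffected.

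**What to change.** Amend the chronology paragraph of SAP Section 7.5.3 as follows.

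1. Show the numbers of AEs resolved and ongoing at last contact by Preferred Term, and state the counting unit (episodes, or first episode per subject).
2. Label the minimum, median and maximum duration as resolved AEs only.
3. For Preferred Terms with enough events, against a threshold set in advance, add a Kaplan-Meier median duration with ongoing AEs censored at last contact. Note that this assumes loss of follow-up is unrelated to remaining duration.
4. For rare terms, list ongoing AEs with duration to last contact, marked with a greater-than sign.

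Borrowing the Section 7.5.1.2 device, with the last visit taken as the stop date, would not be enough. Under uniform onset and exponential durations, a true median of 90 days would then show as about 65, against 58 for resolved AEs only.

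The cost is SAP wording and minor programming. No new data are needed, since start and stop dates are already recorded. Some Kaplan-Meier medians will be reported as not estimable. Items 1 and 2 alone would already stop the table from misleading.
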